### Additional Exclusion Criteria at end of BAE

25. Used any oral or parenteral corticosteroid during the BAE period.

### 4.4 Women of Childbearing Potential

A female is considered to be of childbearing potential (FOCBP) if she has experienced menarche and has not undergone successful sterilisation (e.g. hysterectomy, bilateral tubal ligation or bilateral oophorectomy) or is not postmenopausal. A female is considered to be postmenopausal if amenorrheal for  $\geq 2$  consecutive years.

An effective method of birth control (one with a failure rate of <1% when used correctly) must be used by FOCBP during the course of the study, in a manner such that risk of failure is minimised.

A negative urine pregnancy test is required for all females at Screening Visit 1B/C and prior to each administration of study drug. A pregnancy test will also be conducted at the end of dosing assessment visit (Visit 3I) and at the Follow-Up Visit 5.

Female subjects should be instructed to contact the Investigator immediately if they suspect they might be pregnant.

# 4.5 Rescreening of Subjects

Rescreening of subjects is permitted in a limited number of circumstances for subjects who only failed to qualify for the study because of a criteria which is no longer applicable. The handling of the original and re-screen data for these subjects is described in Section 7.1.1.

VERSION FINAL 4.0 CONFIDENTIAL PAGE 28 OF 92

Subjects who are rescreened will be given a new screening number and will be required to sign a new information sheet and consent form.

#### 4.5.1 Subjects from cold climate sites

Subjects from cold climate sites (Northerly latitudes) whose second dust sample failed to meet the required criteria (see Section 6.2.1.2) but for which all other eligibility criteria were met, may be rescreened and enrolled once the mean average outdoor temperature at the site is above zero degrees Celsius.

Subjects will restart the study at Visit 1A but will only need to repeat certain screening assessments. The assessments to be repeated are shown in Section 6.1. For those assessments that are not repeated, the original data will be used and will need to be transcribed to the new eCRF.

#### 4.5.2 Subjects with Previously Non-Qualifying Specific IgE Levels and/or Skin Prick Test

Versions 1.0 to 3.0, inclusive, of the protocol required subjects to have positive skin prick tests and specific IgE levels of ≥0.7 kU/L to both Der p and Der f. Version 4.0 of the protocol amends this to be a requirement for these assessments to be positive for either Der p or Der f and for a minimum IgE concentration of ≥0.35 kU/L. Subjects who previously failed to qualify for the study because of the original criteria but who now qualify based on the revised criteria may be rescreened and will restart the study at Visit 1A. The blood sample for specific IgE does not need to be repeated; the result from the previous Visit 1A can be entered into the eCRF. There is no time limit for this rescreening for this criteria.

#### 4.6 Withdrawal of Subjects from the Study

The subjects will be informed that they have the right to withdraw from the study on their own accord at any time, for any reason and without having to state their reason and that this will not affect their future management and treatment. When a subject chooses to withdraw from the study, where possible, the Investigator will record a reason according to the following:

- Recovery/no longer experiencing symptoms of HDM allergic rhinoconjunctivitis.
- Lack of therapeutic response.
- Treatment related side effects.
- Unpleasant study procedures.
- Another disease or condition intervenes and prevents continuation in the study.
- External factors unrelated to the study.

**VERSION FINAL 4.0** CONFIDENTIAL **PAGE 29 OF 92**  The subject may also be withdrawn by the Investigator for the following reasons:

DATE 01 APRIL 2015

- Adverse events (AEs), which in the opinion of the Investigator compromises the subject's participation in the study.
- Non-compliance with study procedures.
- Lost to follow-up.
- Withdrawal of consent.
- Protocol violation.
- Termination of the study.
- Pregnancy prior to completion of administration of study medication.
- Deterioration in the subject's signs/symptoms and/or the subject develops a disease or condition prior to completion of administration of study medication that, in the opinion of the Investigator, would compromise the subject's safety in continuing in the study.
- Use of any of the prohibited therapies.

In addition to this list of general criteria for withdrawing subjects from the study dosing should immediately be discontinued (and not restarted) in the event of one or more of the following events:

- A grade 3 or 4 systemic allergic reaction (see Appendix 4)
- Two consecutive doses result in a grade 3 or 4 injection site reaction despite reduction of the dose (See Section 5.5.1)
- A serious adverse event that in the opinion of the Investigator is treatment related
- Medical necessity for a subject to use any of the contraindicated medications (see Section 5.8.5) during the treatment period.

Treatment discontinuation will not necessarily result in withdrawal of the subject from the study. For the subjects who withdraw from the study, all safety assessments scheduled for the Period 3 Follow-Up (Visit 5) (see Section 6.2.3.2) will be requested and observations will be recorded as far as is possible. Reasons for omission of tests will be documented. The date and reason(s), if provided, for withdrawal from the study will also be recorded in the electronic Case Report Form (eCRF).

If the subject withdraws due to an AE, all of the Period 3 Follow-Up (Visit 5) assessments will be requested and the event followed until resolution or care is transferred to the subject's primary care physician or a specialist.

VERSION FINAL 4.0 CONFIDENTIAL PAGE 30 OF 92

Subjects who are withdrawn may be replaced.

# 4.7 Criteria for Stopping the Study

If, in the opinion of an Investigator, the clinical observations in the study suggest that it may be unwise to continue, the Investigator may terminate his or her involvement in the study after consultation with Circassia Ltd.

DATE 01 APRIL 2015

For the study as a whole, Circassia Ltd may terminate the study for safety or administrative reasons.

A Data Safety Monitoring Committee (DSMC) will be convened to provide independent oversight of the trial from a safety perspective (see Section 10.0). The DSMC may recommend stopping of the study for safety reasons and detailed guidance to the DSMC will be provided in the DSMC Charter.

# 4.8 End of the Study

The end of the study is when the last subject completes the Period 3 Follow-Up (Visit 5).

VERSION FINAL 4.0 CONFIDENTIAL PAGE 31 OF 92

### 5.0 STUDY MEDICATION

# 5.1 Investigational Product

The investigational product for this study will be HDM-SPIRE, an equimolar mixture of seven peptides whose individual sequences are derived from Der p1, Der p2 and Der p7, supplied as a lyophilisate. Further details of the peptides are provided in the Investigator's Brochure for HDM-SPIRE. Two concentrations of HDM-SPIRE will be used in the study:

- A 120  $\mu$ M product which will be used for administration of the 12 nmol doses
- A 200  $\mu$ M product which will be used for administration of the 20 nmol dose

The blinded lyophilisate will be reconstituted with water for injection (WFI) as shown in Table 3.

The peptides have been synthesised by Bachem AG (Switzerland) and formulated, filled and finished by Patheon (Italy). All manufacturing processes have been performed according to current Good Manufacturing Practice.

Table 3 Reconstitution of Study Medication and Volume to be Administered

Study Medication	Volume of Water for Injection for Reconstitution	Volume Administered
Lyophilisate	300 μL	100 μL

### 5.2 Placebo

The placebo product is supplied as a lyophilisate with an appearance identical to that of the HDM-SPIRE product. When reconstituted it comprises the vehicle used (see Table 4) to formulate the HDM-SPIRE peptides and its appearance is identical to the reconstituted HDM-SPIRE lyophilisate. The injection volume will also be the same (100 µL).

**Table 4 Nominal Composition of the Vehicle** 

Raw Material	Function	Nominal Concentration
L-Methionine	Antioxidant	5 mM
D-Trehalose dihydrate	Tonicity agent	260 mM
Hydrochloric acid Ammonia	pH adjustment	as needed to pH 4

VERSION FINAL 4.0 CONFIDENTIAL PAGE 32 OF 92

### 5.3 Packaging and Labelling

Individual study packs containing blinded vials of lyophilisate of either HDM-SPIRE or placebo will be provided for each subject. Individual study medication vials and study packs will be labelled in accordance with local regulations and will include subject randomisation numbers. The outer packaging of each study pack will also be labelled in accordance with local regulations and will include a product description or identifier; a product lot number, storage conditions and expiry date; protocol details; sponsor name and address; and subject randomisation numbers.

# 5.4 Supply, Storage and Reconstitution

The Investigator has overall responsibility for all study medication issued to the Investigator's centre. The Investigator may delegate the management of the study medication to a Pharmacist or other qualified team member.

The randomised subject study packs will be shipped to the Investigator together with spares. Medication will be shipped under controlled conditions and a temperature logger will be included. The temperature logger must be returned following the instructions provided. The Investigator or designee will confirm receipt and disposition of the study medication in writing.

The study medication must be kept in an appropriate, limited access, secure storage area at 2 to 25°C until its use or return to Circassia Ltd or its designee for destruction. The temperature in the storage areas will be monitored and recorded daily (minimum and maximum temperature). Copies of temperature logs must be kept in the site study file.

Reconstitution should ideally be performed in an International Organisation for Standardization (ISO) Class 5 (or better), temperature-controlled area on a clean surface and with limited access. Only the required vial of lyophilisate for a single subject dose must be present in the preparation area during reconstitution to avoid any errors. Reconstitution will be achieved by injecting  $300\mu L$  of sterile WFI into the study medication vial.

Warning: Study medication does not contain a preservative. Consequently, reconstitution more than a few hours prior to administration carries the risk of microbial contamination.

Following reconstitution, sufficient time (typically 3-5 minutes) should be allowed for any foaming of the solution to subside. The Investigator or designee should withdraw the necessary volume into the syringe to allow the administration of  $100 \, \mu L$ ; in practice this will be  $180\text{-}250 \, \mu L$  to account for the dead volumes of the needle and syringe. This must not be

VERSION FINAL 4.0 CONFIDENTIAL PAGE 33 OF 92

more than 6 hours after reconstitution is completed. If administration will not be performed within 1 hour after reconstitution, the reconstituted doses must be transferred to and kept at  $5 \pm 3$ °C in injection vials until the point of administration.

Where an ISO Class 5 environment is not available, reconstitution should be performed in a temperature-controlled area on a clean surface and with limited access. In this situation the study medication must be administered within 1 hour of reconstitution.

Unused/excess solutions generated during the preparation of individual subject medication will be kept for accountability purposes. At the end of the study, upon written authorisation by Circassia Ltd, the Investigator will return unused study medication to Circassia Ltd or their designee for destruction. A copy of the completed Drug Accountability Record should be included in the shipment. The unused study medication will be destroyed and a certificate of destruction generated.

The study medication supplied for this study is intended for use only by subjects in this study.

## 5.5 Administration of the Study Medication

The reconstituted study medication will be administered by intradermal injection by the Investigator or designee into the flexor (volar) surface of the forearm. The dose to be administered is  $100 \, \mu L$ .

### 5.5.1 Dose Reduction

In the event that a subject experiences a grade 3 or 4 injection site reaction (see Section 6.2.2.1) or a grade 2 systemic allergic reaction (See Appendix 4) the following dose reduction scheme should be followed:

- On first occurrence of a dose reduction trigger reaction the next dose should be reduced by half. This is achieved by administering a dose of 50  $\mu$ L instead of 100  $\mu$ L.
- If the reduced dose is well tolerated then the subsequent dose should be escalated back to 100  $\mu$ L. If this is well tolerated then further doses should continue to be 100  $\mu$ L.
- If however the full dose is again not well tolerated and a further trigger reaction occurs then the dose should again be reduced to  $50 \,\mu L$  and remain at that dose for the remainder of the study.

VERSION FINAL 4.0 CONFIDENTIAL PAGE 34 OF 92

• If two consecutive half doses are not well tolerated the subject should be withdrawn from the study.

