Period 3, Post-Administration Collection (PAC): The RSS and RMS for efficacy evaluation will be collected during Period 3. There will be 3 PAC periods: PAC1 (Weeks 18-20), PAC2 (Weeks 37-39) and PAC3 (Weeks 50-52). The primary efficacy evaluation period will be PAC3, commencing 50 weeks after randomisation and outside of any and all relevant seasonal allergy periods for the subject. The use of allergy rescue medication during the PAC periods will be according to a pre-specified Rescue Medication Plan (see Appendix 3). Data collected in the periods commencing at 18 weeks (PAC1) and 37 weeks (PAC2) after randomisation will be used for exploratory efficacy analyses.

At the Period 3 Follow-Up Visit 5, 52 weeks from first dosing, subjects will undergo a final safety assessment.

The duration of the study for each subject will be approximately 62 weeks.

VERSION FINAL 4.0 CONFIDENTIAL

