### 6.2.2.2 Visit 3I: End of Dosing Assessment

An End of Dosing Assessment (Visit 3I) will take place 4 weeks (±2 days) after the subject received the last dose of study medication. Subjects who are withdrawn from the study prior to receiving the final dose for any reason will proceed directly to a Period 3 Follow-Up (Visit 5).

At Visit 3I the following procedures and assessments will take place:

- Targeted Physical Examination (guided by findings at screening and emerging AEs).
- Examination of the injection site from Visit 3H.
- Spirometry (FEV1) [asthmatic subjects should not take their short acting bronchodilator for a minimum of 4 hours prior to spirometry].
- Vital Signs (seated or semi-recumbent).
- Clinical laboratory assessments including dipstick urinalysis and blood samples for clinical chemistry and haematology.
- Blood sample will be taken for Der p and Der f specific IgE by ImmunoCAP®.
- Urine pregnancy test (for FOCBP).
- Transfer information from pDiary to eCRF, i.e.:
  - o Home environment changes (see Section 6.3.5).

VERSION FINAL4.0 CONFIDENTIAL PAGE 51 OF 92

- Concomitant Medications.
- o AEs.
- Issue new pDiary.

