#### 6.4.3 Reporting of Pregnancy

Subjects who become pregnant before the start of dosing (from consent to Visit 3A) must be withdrawn from study immediately after the pregnancy is confirmed. Subjects who become

VERSION FINAL4.0 CONFIDENTIAL PAGE 61 OF 92

pregnant during the dosing period must receive no further study treatment and the pregnancy must be reported using the same procedure as for SAEs (see Section 6.4.2). Subjects who become pregnant once dosing has completed may remain in the study and the pregnancy must be reported using the same procedure as for SAEs. Pregnancy will be recorded in the subject's medical files. A Pregnancy Notification Form must be completed and is reported using the same procedure as for the SAEs (see Section 6.4.2). The outcome of the pregnancy will be followed-up until term end, full or premature termination. A Pregnancy Outcome Form, to assess the health of the mother and any infants, will be completed and reported following the same procedure as the notification form.

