## 7.2 Sample Size

The study will recruit approximately 660 subjects (approximately 165 per group). Based on the data from observational study TH003, if a mean CS of 1.6 is observed for the placebo group, and a mean CS of 1.28 for the active group, the expected treatment difference of 0.32 will be a 20% improvement from placebo. The statistical model will include the baseline CS as a covariate, taking this into account a standard deviation of 0.986 is assumed, so that a sample of 150 patients will have 80% power to detect a statistically significant difference in treatment.

Other data sources result in sample size estimates that range from 103/group (based on the TRSS data from Study TH002) through to 200/group (based on symptom scores adjusted for medication use in a study of sublingual HDM immunotherapy [Bergmann et al, 2013]). These data support the assumptions from Study TH003 and indicate that a difference of 20% between placebo and active treatment will be observed with a sample size of 150 subjects per group. It is estimated that up to 10% of subjects may drop-out before PAC3 or have missing data during PAC3. Consequently, approximately 660 subjects in total will be randomised.

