- Completed the study, early withdrawal from the study as well as primary reason for early withdrawal from the study as entered on the End of Study eCRF (EOS)

Completed the study is defined as completing the Follow-up Period (Visit 5) without prior early withdrawal from the study as indicated on the End of Study eCRF (EOS), regardless of completion of study medication as indicated on the End of Treatment eCRF (EOT). The frequency (n) and percentage (%) of subjects assigned to each analysis population is to be provided for the Randomized, ITT, PP and SAF populations, as well the reasons for exclusion from each population.

Percentages are to be calculated relative to the total number of subjects in the analysis population.

The following listings are planned for presentation:

- Subjects screening status (ENR population)
  - Includes eligibility criteria and inclusion/exclusion criteria exceptions
- Subject disposition (RND population)
- Analysis population assignment (ENR population)
- Major protocol deviations (RND population)

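### Protocol 5.5.1 directs study withdrawal after two failed half doses where 4.6 only stops dosing, so PAC3 may go uncollected for a few ITT subjects (low severity, cheap to fix)

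*Protocol*

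**What the plan says.** Protocol 5.5.1 halves the next dose after a grade 3 or 4 injection-site reaction or a grade 2 systemic allergic reaction. Its last step reads: "If two consecutive half doses are not well tolerated the subject should be withdrawn from the study".

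Protocol 4.6 has a separate list of events after which dosing must stop and not restart. One item, which cross-refers to 5.5.1, is: "Two consecutive doses result in a grade 3 or 4 injection site reaction despite reduction of the dose". For systemic reactions the list names grades 3 and 4 only. The text after the list says: "Treatment discontinuation will not necessarily result in withdrawal of the subject from the study". The same section allows withdrawn subjects to be replaced.

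Protocol 6.2.2.2 sets out what follows a withdrawal during dosing: "Subjects who are withdrawn from the study prior to receiving the final dose for any reason will proceed directly to a Period 3 Follow-Up". That follow-up is Visit 5. Under 4.6, what is requested of a withdrawn subject is the Visit 5 assessments.

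The ITT population (Protocol 7.4.1, SAP 5.3) is everyone randomised who received at least one dose. The primary MMRM (Protocol 7.5.3.1.1, SAP 15.1.3) uses the PAC1, PAC2 and PAC3 means under missing at random, without imputation. SAP 15.1.4 adds a control-based multiple imputation as a sensitivity analysis. Protocol 7.2 allows for losses: "It is estimated that up to 10% of subjects may drop-out before PAC3 or have missing data during PAC3".

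**The concern.** Two sites could meet the same tolerability event and act differently, each following the protocol. One stops the injections and keeps the subject filling in diaries. The other removes the subject from the study and loses PAC3.

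Stopping injections deals with the safety problem. Ending diary collection adds no protection and gives up a primary outcome that could still be recorded. The trigger is a reaction to the injection, so the loss could differ between active and placebo arms. A subject lost before PAC1 contributes nothing to the primary MMRM.

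Repeated grade 2 systemic reactions fall further outside 4.6. They trigger dose reduction under 5.5.1 but are not on the dosing-stop list, so for them study withdrawal is the only specific instruction.

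**Working it through.** **Timing.** Protocol Table 2 puts active injections at weeks 0, 4, 8 and 12 in the two 4-dose arms, and at weeks 0 to 28 in the 8 x 12 nmol arm. PAC1 is weeks 18-20, PAC2 weeks 37-39 and PAC3 weeks 50-52. The shortest route to the 5.5.1 rule is one full-dose reaction and then two failed half doses, so three trigger reactions.

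- 4-dose arms, all reactions to active injections: a full-dose reaction at week 0 is followed by failed half doses at weeks 4 and 8; one at week 4 by failed half doses at weeks 8 and 12. The rule is met at the week 8 or week 12 dose. A reaction to the week 12 dose is seen at the week 16 visit at the latest, before PAC1 opens at week 18. The subject has a baseline score only.
- 8 x 12 nmol arm: the rule can also be met later. From the week 20 dose on, PAC1 has ended (Visit 4B coincides with the week 20 dosing visit), so such subjects may already have PAC1 data and enter the MMRM. Week 28 is the final dose, so a case arising there is outside the 6.2.2.2 sentence on withdrawal before the final dose.

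**The plan's own figure.** Inputs from Protocol 7.2: difference 0.32 (1.6 against 1.28), SD 0.986, 150 per group, two-sided 0.05. SE = 0.986 × √(2/150) = 0.114. Two-sample t power = 80.0%, which reproduces the stated 80%.

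**Size under an assumed rate.** The documents give no rate. I take 1% and 5% of an active arm of 165 to show a range: 0.01 × 165 = 1.65 and 0.05 × 165 = 8.25 subjects. Zero is also possible. Placebo stays at 150.

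| Scenario | Inputs at 1% | Power | Inputs at 5% | Power |
|---|---|---|---|---|
| Inside the 10% allowance | n = 150, effect 0.32 | 80.0% | n = 150, effect 0.32 | 80.0% |
| Lost on top of the 10%, not replaced | n = 150 − 1.65 = 148.35 | 79.8% | n = 150 − 8.25 = 141.75 | 78.9% |
| Retained, no benefit | effect 0.32 × 0.99 = 0.3168 | 79.2% | effect 0.32 × 0.95 = 0.304 | 75.9% |
| Retained, half benefit | effect 0.32 × 0.995 = 0.3184 | 79.6% | effect 0.32 × 0.975 = 0.312 | 78.0% |
| Retained, full benefit | effect 0.32 | 80.0% | effect 0.32 | 80.0% |

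**Effect of omitting them.** If these subjects have no benefit and the rest of the arm has 0.32, an estimate that leaves them out exceeds the ITT effect by:

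- 1%: 0.32 − 0.3168 = 0.0032, and 0.0032/0.114 = 0.03 SE
- 5%: 0.32 − 0.304 = 0.016, and 0.016/0.114 = 0.14 SE

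**The case against.** The best reply is that the sections can be followed together: stop dosing under 4.6, then apply the more specific 5.5.1. That stands. A reader might infer a flat contradiction, but the 4.6 sentence says stopping treatment does not always mean withdrawal, which leaves room for it. The difference is between directed and discretionary withdrawal.

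Second, the size is small. Three trigger reactions are needed, doses up to 12 nmol were well tolerated earlier (Protocol 1.2), the 10% allowance may already cover the losses, and withdrawn subjects may be replaced. All of this stands, with two limits: 20 nmol had not been studied before (Protocol 1.3.1), and replacement restores numbers but not the outcomes of the subjects who were lost.

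Third, SAP 15.1.4 already imputes missing active-arm values from placebo, including for subjects with only a baseline score. That does address the no-benefit case. It does so by assumption and in a sensitivity analysis; diaries would show what happened.

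Fourth, the change can cost power: 75.9% against 78.9% at an assumed 5% with no benefit. That is correct, and it is why power is not the argument.

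A reader might also cite pregnancy as a precedent, because Protocol 6.4.3 says subjects who become "pregnant during the dosing period must receive no further study treatment". It does not serve. Section 4.6 lists pregnancy before the end of dosing among the reasons for withdrawal, and 6.2.2.1 requires a negative test for the subject to continue in the study.

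**Conclusion.** This is a low-severity wording inconsistency worth correcting because the correction is cheap. The text supports one specific consequence: an ITT subject withdrawn under 5.5.1 before the final dose has no PAC3 data and, if the rule is met by the week 12 dose, no post-baseline combined score.

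The number of such subjects is unknown, probably small and possibly zero. On the assumed 1% to 5% of an active arm, and if they have no benefit, omitting them shifts the estimate by 0.03 to 0.14 SE. The gain from the change is observed rather than assumed ITT outcomes.

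Two stronger readings are not supported. A reader might infer that the primary result is biased or the trial underpowered; no document gives a rate or a difference between arms, and planned power is 80.0% if the allowance covers the losses. A reader might also extend the point to contraindicated drugs, since 4.6 stops dosing for medical need of one while 5.8.5 (Period 2) and 11.0 direct study withdrawal. That wording does differ, but no bias is shown by that route. Nor does the item in 4.6 that lets the investigator withdraw users of prohibited therapies clearly refer to these drugs, because 5.8.5 applies that term to starting other immunotherapy.

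**What to change.** 1. In 5.5.1, replace study withdrawal with permanent discontinuation of study medication.
2. In the 4.6 dosing-stop list, add repeated grade 2 systemic reactions despite dose reduction.
3. State in 4.6 that subjects who stop dosing and keep their consent continue the scheduled PAC1 to PAC3 eDiaries and questionnaires.

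Section 6.2.2.2 can stay as it is for true study withdrawals. The SAP needs no change for this: Section 9 already counts study completion separately from completion of dosing, on separate End of Treatment and End of Study forms. Aligning 5.8.5 and 11.0 with the 4.6 dosing-stop item for contraindicated drugs is optional tidying.

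The cost is a protocol amendment, diary follow-up of a few off-treatment subjects at visits already scheduled, and slight dilution of the ITT effect if they have no benefit (power 79.2% to 75.9% at the assumed 1% to 5%). The sample size does not change.
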